Appendix E Imputation Rules for Missing Prior/Concomitant Medication Dates

The following rules will be applied for every treatment-emergent period:

Imputation rules for missing or partial medication start/stop dates are defined below:

- Missing or partial medication start date:
 - If only DAY is missing, use the first day of the month.
 - If DAY and Month are both missing, use the first day of the year.
 - If DAY, Month and Year are all missing, use a date before the first dose date.
- Missing or partial medication stop date:
 - If only DAY is missing, use the last day of the month.
 - If DAY and Month are both missing, use the last day of the year.
 - If DAY, Month and year are all missing, leave the stop date as missing; the medication will be considered ‘continuing’ at the study exit.

In summary, the prior, concomitant or post categorization of a medication is described below.

Table 13-6 Prior, Concomitant, and Post Categorization of a Medication

Medication Start Date	Medication Stop Date		
	< First Dose Date of Study Drug	≥ First Dose Date and ≤ End Date of Treatment-Emergent Period	> End Date of Treatment-Emergent Period
< First dose date of study drug	P	PC	PCA
≥ First dose date and ≤ End date of Treatment-Emergent period	-	C	CA
> End date of Treatment-Emergent period	-	-	A

A: Post; C: Concomitant; P: Prior

Appendix F Coefficients for Wang Methods for Calculating Predicted Spirometry Parameters

Percent predicted FEV₁ is the ratio of FEV₁ (L) to the predicted FEV₁ (L), expressed as a percentage. The predicted FEV₁ (L) will be calculated using the Hankinson¹ and Wang² standards.

The Wang standard applies to male subjects 6 to 17 years and female subjects 6 to 15 years of age. Wang's standard will be used to calculate the predicted spirometry parameters for the population enrolled in to this study.

Wang Normal Values (WNVs) will be calculated for FEV₁, FVC, FEF_{25-75%}, and FEV₁/FVC using the Wang equation:

$$\ln(\text{Predicted lung function parameter}) = \alpha + \beta \ln(\text{height})$$

WNVs will be calculated for FEV₁, FVC, FEF_{25-75%}, and FEV₁/FVC using the Wang equation. In the equation, height is given in meters, and the coefficients α and β are determined based on subject's sex, race, and age as shown in Table 13-7 and Table 13-8.

If either height or age is missing, and the spirometry measurement is non-missing, the last non-missing value of height and age will be used in the calculation of predicted values.

Table 13-7 WNVs Equation Coefficients by Sex and Age in White Boys and Girls

Sex	Age	FEV ₁		FVC		FEF _{25-75%}		FEV ₁ /FVC	
		α	β	α	β	α	β	α	β
Male	6	-0.109	2.252	-0.024	2.470			-0.078	-0.248
	7	-0.104	2.270	-0.018	2.489			-0.086	-0.220
	8	-0.089	2.257	0.005	2.443	0.264	1.505	-0.091	-0.199
	9	-0.063	2.197	0.017	2.426	0.308	1.443	-0.086	-0.206
	10	-0.057	2.212	0.030	2.407	0.290	1.557	-0.081	-0.209
	11	-0.093	2.324	0.009	2.468	0.242	1.738	-0.101	-0.147
	12	-0.161	2.512	-0.061	2.649	0.165	1.982	-0.101	-0.133
	13	-0.292	2.843	-0.175	2.924	0.007	2.396	-0.116	-0.085
	14	-0.329	2.983	-0.219	3.060	0.014	2.483	-0.106	-0.087
	15	-0.141	2.709	-0.079	2.859	0.241	2.163	-0.060	-0.155
	16	0.062	2.409	0.104	2.591	0.503	1.764	-0.045	-0.178
17	0.262	2.099	0.253	2.374	0.762	1.368	0.008	-0.272	
Female	6	-0.109	1.949	-0.013	2.007			-0.097	-0.055
	7	-0.144	2.243	-0.062	2.385			-0.084	-0.132
	8	-0.137	2.239	-0.055	2.381	0.247	1.668	-0.079	-0.152
	9	-0.123	2.222	-0.039	2.351	0.254	1.710	-0.084	-0.128
	10	-0.161	2.364	-0.068	2.458	0.195	1.933	-0.092	-0.097
	11	-0.223	2.558	-0.120	2.617	0.161	2.091	-0.102	-0.061
	12	-0.264	2.709	-0.174	2.776	0.185	2.120	-0.090	-0.067
	13	-0.153	2.535	-0.061	2.576	0.294	1.976	-0.093	-0.040
	14	0.046	2.178	0.139	2.208	0.450	1.711	-0.096	-0.026
	15	0.148	2.008	0.210	2.099	0.581	1.486	-0.062	-0.093

Source: Reference 1 (Tables 2 and 3)

Table 13-8 WNVs Equation Coefficients by Sex and Age in Black Boys and Girls

Sex	Age	FEV ₁		FVC		FEF _{25-75%}		FEV ₁ /FVC	
		α	β	α	β	α	β	α	β
Male	6	-0.166	1.723	-0.088	1.961			-0.091	-0.152
	7	-0.122	1.846	-0.040	2.040			-0.091	-0.153
	8	-0.225	2.271	-0.094	2.323	0.097	1.544	-0.118	-0.104
	9	-0.142	2.059	-0.074	2.308	0.255	1.248	-0.079	-0.218
	10	-0.157	2.117	-0.110	2.417	0.230	1.428	-0.047	-0.303
	11	-0.176	2.166	-0.138	2.453	0.256	1.438	-0.048	-0.263
	12	-0.307	2.548	-0.224	2.710	0.085	1.936	-0.084	-0.162
	13	-0.486	2.962	-0.342	2.975	-0.121	2.476	-0.141	-0.018
	14	-0.472	3.010	-0.337	3.035	-0.115	2.536	-0.123	-0.050
	15	-0.318	2.789	-0.226	2.889	0.170	2.120	-0.070	-0.140
	16	0.074	2.140	0.058	2.425	0.663	1.299	0.018	-0.289
17	0.053	2.223	0.148	2.310	0.505	1.618	-0.095	-0.087	
Female	6	-0.288	2.182	-0.172	2.117			-0.109	0.059
	7	-0.250	2.158	-0.135	2.132			-0.104	-0.030
	8	-0.276	2.295	-0.176	2.362	-0.283	2.990	-0.103	-0.066
	9	-0.294	2.330	-0.200	2.452	0.025	2.062	-0.097	-0.104
	10	-0.344	2.507	-0.230	2.571	0.051	2.028	-0.120	-0.043
	11	-0.308	2.460	-0.204	2.526	0.078	2.006	-0.089	-0.105
	12	-0.219	2.312	-0.107	2.342	0.225	1.804	-0.115	-0.021
	13	-0.117	2.196	-0.042	2.294	0.418	1.504	-0.051	-0.148
	14	0.041	1.920	0.105	2.021	0.574	1.257	-0.063	-0.103
	15	0.203	1.662	0.253	1.787	0.599	1.281	-0.043	-0.139

Source: Reference 2 (Tables 4 and 5)

Appendix H Criteria for Threshold Analysis

Table 13-9 Threshold Analysis Criteria for Laboratory Tests

Parameter	Threshold Analysis	Comments
Clinical Chemistry		
ALT	$\leq 3xULN$ $>3x - \leq 5xULN$ $>5x - \leq 8xULN$ $>3xULN$ $>5xULN$ $>8xULN$	FDA DILI Guidance Jul 2009.
AST	$\leq 3xULN$ $>3x - \leq 5xULN$ $>5x - \leq 8xULN$ $>3xULN$ $>5xULN$ $>8xULN$	FDA DILI Guidance Jul 2009.
ALT or AST	ALT>3xULN or AST>3xULN	Vertex LFT working group 2014
Alkaline Phosphatase	>1.5xULN	FDA DILI Guidance Jul 2009.
Total Bilirubin	$>1.5x - \leq 2xULN$ $>2xULN$	FDA DILI Guidance Jul 2009.
ALT and Total Bilirubin	ALT>3xULN and TBILI>2xULN	FDA DILI Guidance Jul 2009. To be counted within a same treatment phase, whatever the interval between measurement.
AST and Total Bilirubin	AST>3xULN and TBILI>2xULN	FDA DILI Guidance Jul 2009. To be counted within a same treatment phase, whatever the interval between measurement.
(ALT or AST) and Total Bilirubin	(ALT>3xULN or AST>3xULN) and TBILI>2xULN	Vertex LFT working group 2014
CPK	$>3x - \leq 10xULN$ $>10xULN$	FDA Feb 2005. Am J Cardiol April 2006.
Creatinine	$\geq 150 \mu\text{mol/L}$ (Adults) $\geq 30\%$ change from baseline $\geq 100\%$ change from baseline	Benichou C., 1994.
Creatinine Clearance (Cockcroft's formula)	<30 ml/min (severe renal impairment) $\geq 30 - <50$ ml/min (moderate renal impairment) $\geq 50 - \leq 80$ ml/min (mild renal impairment)	FDA criteria May 1998.
Uric Acid		Harrison- Principles of internal Medicine 17 th Ed., 2008.
Hypouricemia	<120 $\mu\text{mol/L}$	
Hyperuricemia	>408 $\mu\text{mol/L}$	
Blood Urea Nitrogen	≥ 17 mmol/L	
Chloride	<85 mmol/L >115 mmol/L	
Sodium	≤ 129 mmol/L ≥ 150 mmol/L	

Table 13-9 Threshold Analysis Criteria for Laboratory Tests

Parameter	Threshold Analysis	Comments
Potassium	<3 mmol/L ≥5.5 mmol/L	FDA Feb 2005.
Total Cholesterol	≥7.74 mmol/L	Threshold for therapeutic intervention.
Triglycerides	≥4.6 mmol/L	Threshold for therapeutic intervention.
Glucose		
Hypoglycaemia	≤3.9 mmol/L and <LLN	ADA May 2005.
Hyperglycaemia	≥11.1 mmol/L (unfasted); ≥7 mmol/L (fasted)	ADA Jan 2008.
HbA1c	>8%	
Albumin	≤25 g/L	
CRP	>2xULN or >10 mg/L (if ULN not provided)	FDA Sept 2005.
Hematology		
WBC	<3.0 Giga/L (Non-Black); <2.0 Giga/L (Black) ≥16.0 Giga/L	Increase in WBC: not relevant. To be interpreted only if no differential count available.
Lymphocytes	>4.0 Giga/L	
Neutrophils	<1.5 Giga/L (Non-Black); <1.0 Giga/L (Black)	International Consensus meeting on drug-induced blood cytopenias, 1991. FDA criteria.
Monocytes	>0.7 Giga/L	
Basophils	>0.1 Giga/L	
Eosinophils	>0.5 Giga/L or >ULN (if ULN ≥0.5 Giga/L)	Harrison- Principles of internal Medicine 17 th Ed., 2008.
Hemoglobin	≤115 g/L (Male); ≤95 g/L (Female) ≥185 g/L (Male); ≥165 g/L (Female) Decrease from Baseline ≥20 g/L	Criteria based upon decrease from baseline are more relevant than based on absolute value. Other categories for decrease from baseline can be used (≥30 g/L, ≥40 g/L, ≥50 g/L).
Hematocrit	≤0.37 v/v (Male) ; ≤0.32 v/v (Female) ≥0.55 v/v (Male) ; ≥0.5 v/v (Female)	
RBC	≥6 Tera/L	
Platelets	<100 Giga/L ≥700 Giga/L	International Consensus meeting on drug-induced blood cytopenias, 1991.

Table 13-10 Threshold Analysis Criteria for ECGs

CRITERIA for THRESHOLD ANALYSIS of ECGs		
Ref.: CPMP 1997 guideline.		
Parameter	Threshold Analysis	Comments
HR	≤ 50 bpm and decrease from baseline ≥ 20 bpm ≥ 120 bpm and increase from baseline ≥ 20 bpm	
PR	≥ 220 ms and increase from baseline ≥ 20 ms	
QRS	≥ 120 ms	
QTc	Absolute values (ms)	To be applied to any kind of QT correction formula.
Borderline	Borderline: 431-450 ms (Male); 451-470 ms (Female)	
Prolonged*	Prolonged: >450 ms (Male); >470 ms (Female)	
Additional	≥ 500 ms	
	Increase from baseline	
	Borderline: Increase from baseline 30-60 ms	
	Prolonged: Increase from baseline >60 ms	

Table 13-11 Threshold Analysis Criteria for Vital Signs

CRITERIA for THRESHOLD ANALYSIS of VITAL SIGNS		
Parameter	Threshold Analysis	Comments
HR	≤ 50 bpm and decrease from baseline ≥ 20 bpm ≥ 120 bpm and increase from baseline ≥ 20 bpm	To be applied for all positions (including missing) except STANDING.
SBP	≤ 95 mmHg and decrease from baseline ≥ 20 mmHg ≥ 160 mmHg and increase from baseline ≥ 20 mmHg	To be applied for all positions (including missing) except STANDING.
DBP	≤ 45 mmHg and decrease from baseline ≥ 10 mmHg ≥ 110 mmHg and increase from baseline ≥ 10 mmHg	To be applied for all positions (including missing) except STANDING.
Orthostatic Hypotension		
Orthostatic SBP	≤ -20 mmHg	
Orthostatic DBP	≤ -10 mmHg	
Weight	$\geq 5\%$ increase from baseline $\geq 5\%$ decrease from baseline	FDA Feb 2007.

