11.7.3 Elevation of Liver Function Test Parameters

It is strongly recommended that subjects with new ALT or AST elevations of $\geq 3 \times \text{ULN}$ and clinical symptoms be followed closely, including repeat confirmatory testing performed by the central laboratory within 48 to 72 hours of the initial finding and subsequent close monitoring of ALT and AST levels, as clinically indicated.

Study Drug Interruption

Study drug administration **must be interrupted** immediately, and the Vertex medical monitor or designee must be notified, if any of the following criteria is met:

- ALT or AST $\geq 8 \times \text{ULN}$
- ALT or AST $\geq 5 \times \text{ULN}$ for more than 2 weeks
- ALT or AST $\geq 3 \times \text{ULN}$ in association with total bilirubin $\geq 2 \times \text{ULN}$ and/or clinical jaundice

A thorough investigation of potential causes should be conducted and the subject should be followed closely for clinical progression.

If no convincing alternative etiology (e.g., acetaminophen use, viral hepatitis, or alcohol ingestion) for the elevated transaminases is identified, regardless of whether ALT or AST levels have improved, study drug treatment must be discontinued, in consultation with the Vertex medical monitor or authorized designee. Subjects in whom treatment is discontinued for elevated transaminases should have their transaminases monitored closely until levels normalize or return to baseline.

Resumption of Study Drug

If a convincing alternative etiology is identified for the elevated transaminases (ALT, AST, and total bilirubin), study drug may be resumed when transaminases return to baseline or are $\leq 2 \times \text{ULN}$, whichever is higher. Approval of the Vertex medical monitor or designee is required before resumption of study drug. Upon resumption of study drug, transaminases should be assessed weekly for 4 weeks. If a protocol-defined transaminase elevation occurs within 4 weeks of rechallenge with the study drug, then the study drug must be discontinued, regardless of the presumed etiology.

Mandatory Liver Function Testing

Liver function testing (ALT, AST, gamma glutamyl transpeptidase, alkaline phosphatase, and total bilirubin) must be performed while subjects are receiving study drug treatment (Day 1, Day 15, and at a minimum of every 4 weeks after Week 4 as noted in [Table 3-1](#)). These blood samples should be processed and shipped immediately per the Laboratory Manual.

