12.4.4.2 Clinical Laboratory Assessments

A summary of raw values and change from baseline values at each visit will be provided for the continuous laboratory results in SI units for current dosing period based on Study 110 Safety Set, and for the active dosing period based on the Integrated Safety Set. For each of the LFTs, mean values will be plotted against visit by treatment arm.

The number and percentage of subjects with shift changes from baseline (normal/missing, high, low, according to the reference range), based on the worst on-treatment laboratory evaluation, will be tabulated.

For subjects with at least 1 potentially clinically significant (PCS) event during the treatment-emergent period, summaries will be presented for each elevation category using number and percentage of subjects as well as number of elevations per 100 patient-year

(number of elevations adjusted for the total duration of exposure). The PCS criteria will be provided in the SAP.

A listing of subjects with elevated LFT results during the treatment-emergent period will be presented including all parameters of the liver function and assessment at all visits.

Results of pregnancy tests will be listed in individual subject data listings only. In addition, a listing containing individual subject laboratory values outside the reference ranges will be provided. This listing will include data from scheduled and unscheduled time points.

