10.1.2 Safety Analysis Presentation Rules and Format

10.1.2.1 Event Data

Treatment Cohort Period 1

Unless otherwise specified, incidence tables summarizing n and percentages for categorical safety data will be provided for:

- Previous Study Period (Studies 109/011B) based on the Safety Set with two treatment groups (L200/I, Placebo);
- Current Study Period (Study 110) based on the 110 Safety Set with two treatment groups (L200/I-L/I, P-L/I) and Overall;
- Cumulative Study Period based on Safety Set with L200/I-L/I, and Current Study Period based on 110 Safety Set with P-L/I, pooled together. The pooled treatment group is presented as L/I Overall.

Exposure-adjusted number of events will summarize number of events per 100 patient-year (100PY) for AE related safety data. Note: 1 patient with 48 weeks of exposure duration is defined as 1 patient-year (1PY). The exposure-adjusted number of events will be provided for the Study Periods with the analyses sets and treatment groups as defined above.

The categorical safety summary tables with incidence only will be presented in the table format as shown in Table 10-3. The categorical safety summary tables with both incidence and

exposure-adjusted number of events summaries will be presented in the table format as shown in Table 10-4.

Table 10-3 Presentation Format for Summary Tables of Categorical Safety Endpoints with Incidence Summary Only

109/011B		110			109/011B and 110	
L200/I	Placebo	L200/I-L/I	P-L/I	Overall	L/I Overall	

Table 10-4 Presentation Format for Summary Tables of Categorical Safety Endpoints with Both Incidence and Exposure-Adjusted Number of Events Summaries

109/011B				110				109/011B and 110			
L200/I		Placebo		L200/I-L/I		P-L/I		Overall		L/I Overall	
n (%)	Events/100PY	n (%)	Events/100PY	n (%)	Events/100PY	n (%)	Events/100PY	n (%)	Events/100PY	n (%)	Events/100PY

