10.4.2 Clinical Laboratory

Treatment Cohort Period 1

For the laboratory measurements, the raw values and change from previous study baseline of the continuous hematology and chemistry results will be summarized in System International (SI) units at each scheduled time point in the Cumulative Study Period based on the Safety Set.

The number and percentage of subjects meeting the defined threshold criteria during the treatment-emergent period will be summarized. The threshold criteria are provided in Appendix H. For LFT results (alanine aminotransferase [ALT], aspartate aminotransferase [AST], serum alkaline phosphatase [ALP], and total bilirubin), the following analyses will be conducted:

- The mean values (95% CI) will be plotted against visit for all the visits in the Cumulative Study Period for ALT and AST.

- A listing for subjects with elevated LFT results during the treatment-emergent period of the Cumulative Study Period will be presented. The listing will include all parameters of the LFT assessment at all visits.

The number and percentage of subjects with shift changes from baseline in ALT, AST, ALP and total bilirubin (normal/missing, high, low, according to the reference range), based on the worst on-treatment laboratory evaluation, will be tabulated.

Results of urinalysis and the serum pregnancy test will be listed in individual subject data listings only. A listing containing individual subject hematology, chemistry, and coagulation values will be provided with a column indicating outside reference range or not. This listing will include data from scheduled and unscheduled time points.

Treatment Cohort Period 2

For Treatment Cohort Period 2 LFT results (ALT, AST, ALP, and total bilirubin), the following analyses will be conducted:

- The number and percentage of subjects meeting the defined threshold criteria during the treatment-emergent period of Treatment Cohort Period 2 will be summarized. The threshold criteria are provided in Appendix H.
- A listing for subjects with all LFT results during the treatment-emergent period of the Treatment Cohort Period 2 will be presented. The listing will include all parameters of the LFT assessment at all visits.

Results of urine pregnancy test will be listed in individual subject data listing.

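### The combined ALT/AST and bilirubin rows pair elevations at any interval, so chance pairs grow faster than the number of tests and raise the longer LUM/IVA columns relative to 24-week placebo

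*SAP*

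**What the plan says.** Table 13-9 in SAP Appendix H has three combined liver rows. The ALT-with-bilirubin and AST-with-bilirubin rows carry the comment "To be counted within a same treatment phase, whatever the interval between measurement". The third row, for either transaminase with bilirubin, carries only a source note. The SAP does not define a treatment phase; section 9 works with Study Periods and their treatment-emergent periods.

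SAP 10.4.2 sets the measure: "The number and percentage of subjects meeting the defined threshold criteria during the treatment-emergent period will be summarized". Unless a section says otherwise, SAP 10.1.2.1 and Table 10-3 set the columns:
- L200/I and Placebo in the parent studies
- L200/I-L/I, P-L/I and Overall in Study 110
- a last column that joins cumulative L200/I-L/I data to current-period P-L/I data: "The pooled treatment group is presented as L/I Overall"

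Exposure adjustment in the SAP is narrower than in the protocol. SAP 10.1.2.1 says "Exposure-adjusted number of events will summarize number of events per 100 patient-year (100PY) for AE related safety data", which leaves out laboratory thresholds. Protocol 12.4.4.2 had planned that "summaries will be presented for each elevation category using number and percentage of subjects as well as number of elevations per 100 patient-year".

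**The concern.** Under the any-interval rule, a transaminase rise early in treatment and an unrelated bilirubin rise many months later make one combined case. The chance of such a pairing depends on how long, and how often, a child is tested. Placebo children have 24 weeks. Study 110 adds up to 96 weeks, and children on active drug from the start have up to about 120 weeks.

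Long-term safety is the primary objective, and this row is one where very few cases are expected, so one or two chance pairs can change how it reads. The side-by-side percentages could show combined elevations on LUM/IVA and none on placebo partly because the windows differ in length.

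**Working it through.** The documents give no figure for this criterion, so there is none to reproduce. The check compares expected chance pairs by column length.

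**Inputs from the documents**
- Placebo phase of 24 weeks (Protocol 8.2.1); Study 110 dosing to Week 96; cumulative 24 + 96 = 120 weeks.
- LFT schedule (SAP Table 13-1): Day 15 and Weeks 4, 8, 12, 16, 20, 24 make 7 post-baseline tests. Weeks 36, 48, 60, 72, 84, 96 add 6, giving 13.
- About 200 subjects from Study 109 and 56 from Study 011B (SAP 7.2).
- One patient-year is 48 weeks (SAP 10.1.2.1).

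**Assumptions not in the documents**
- The parent studies also had 7 tests, so 120 weeks has 7 + 13 = 20.
- Study 109 was split 1:1, so L/I Overall has 100 + 56 = 156 subjects at 120 weeks and 100 at 96 weeks, all fully followed.
- All elevation rates.

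**Model 1: short-lived elevations, independent at each of m tests**

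Any interval: P = [1 − (1 − pA)^m] × [1 − (1 − pB)^m]. Same sample: P = 1 − (1 − pA·pB)^m.

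With pA = 1% (ALT/AST) and pB = 0.1% (bilirubin):

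| Window | m | Any interval | Ratio | Same sample | Ratio |
|---|---|---|---|---|---|
| 24 weeks | 7 | 0.0474% | 1 | 0.007% | 1 |
| 96 weeks | 13 | 0.1583% | 3.34 | 0.013% | 1.86 |
| 120 weeks | 20 | 0.3607% | 7.61 | 0.020% | 2.86 |

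Expected chance pairs in L/I Overall:
- Any interval: 156 × 0.3607% + 100 × 0.1583% = 0.72.
- Same sample: 156 × 0.020% + 100 × 0.013% = 0.044.
- Placebo, any interval: 0.047 per 100 subjects.

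Over per-test rates from 0.5%/0.1% to 3%/1%, the any-interval ratios are 3.1 to 3.4 at 96 weeks and 6.4 to 7.9 at 120 weeks. The limits for rare events are (13/7)² = 3.45 and (20/7)² = 8.16. For L/I Overall as pooled, the ratio to placebo is 5.1 to 6.1. Across that range, expected any-interval pairs run from 0.4 to 17 in 256 subjects, against 0.02 to 1.3 per 100 on placebo.

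**Model 2: independent elevations at constant rates a and b, always detected**

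P = [1 − exp(−aT)] × [1 − exp(−bT)]. With a = 0.10 and b = 0.02 per 48 weeks, P is 0.0485%, 0.711% and 1.079% at 24, 96 and 120 weeks, so the ratios are 14.7 and 22.2. Over a = 0.05 to 0.15 and b = 0.01 to 0.03 they are 14.0 to 15.3 and 21.0 to 23.6. With shared susceptibility between the two markers (gamma frailty, variance 0.5 to 5) they fall to 8.7 to 13.6 and 11.6 to 20.1.

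**If a phase means each study separately**

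Under model 1 at 1%/0.1%, a continuously treated child has about 0.0474% + 0.1583% = 0.2057%, which is 4.3 times the 24-week value. L/I Overall then expects 156 × 0.2057% + 100 × 0.1583% = 0.48. The direction stays; the size falls.

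**Per patient-year**

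Under model 1 the limiting ratios become 3.45/4 = 0.86 and 8.16/5 = 1.63. Under model 2 they stay at 3.5 to 3.8 and 4.2 to 4.7.

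**The case against.** An any-interval count is a sensitive screen, and sensitivity is a reasonable aim for a liver signal. Safety is descriptive, so no test is invalidated. SAP 10.4.2 lists all LFT parameters at all visits for subjects with elevated results, and SAP 10.5 gives narrative listings for the combined elevation, so a spurious pair can be recognised. Table 10-3 also has a 24-week L200/I column beside placebo, which phase length does not affect, although it pools uncontrolled Study 011B with Study 109. Eligibility and discontinuation rules may thin late pairings further. All of this stands. It limits the harm, but case review does not correct the percentages in the table.

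Three stronger readings are tempting and not supported:
- A reader might infer that chance pairs rise with the square of phase length. That needs rare, independent elevations that are always detected. Testing thins from every 4 to every 12 weeks after Week 24, and short-lived elevations then follow roughly the square of the number of tests.
- A reader might infer that a patient-year rate cannot help. Under model 1 it removes most of the effect; under model 2 it does not.
- A reader might see a contradiction with Protocol 11.7.3, which speaks of a transaminase rise "in association with total bilirubin". That passage governs drug interruption, uses different limits and states no interval. Protocol 12.4.4.2 left the analysis criteria to the SAP.

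**Conclusion.** The concern holds in direction under every model run: without exposure adjustment, the any-interval rule inflates the longer LUM/IVA columns relative to 24-week placebo. The size is uncertain because the documents give no elevation rates. On the actual schedule, about 3-fold at 96 weeks and 6- to 8-fold at 120 weeks is the figure for short-lived elevations; about 15- and 22-fold is the upper end. L/I Overall is only partly a 120-week column.

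Part of the growth comes from longer testing alone: same-sample pairs also rise 1.9- and 2.9-fold. Only the excess belongs to this rule. That excess still supplies most chance pairs, about 0.72 against 0.04 expected cases in 256 subjects at 1%/0.1% per test. These figures assume 7 parent-study tests, 1:1 allocation and full follow-up. The undefined phase and the silent third row add avoidable ambiguity in programming.

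**What to change.** In SAP Table 13-9:
- Keep the any-interval count and label it as a sensitive screen.
- Add a row for ALT or AST above 3×ULN with total bilirubin above 2×ULN on the same sample date.
- State that the treatment phase is the treatment-emergent period of the column's Study Period, and apply one timing rule to all three existing combined rows.

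In the LFT listing (SAP 10.4.2) and the narrative listing (SAP 10.5), show the days between the two elevations.

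The cost is SAP wording, one table row and one derived variable. No case is lost, because the screening row stays. The drawback is that, with 12-weekly testing after Week 24, a bilirubin rise that lags the transaminase rise appears only in the screening row; the interval in the listings makes it visible.
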